## **E. EXPERIMENTAL DESIGN & METHODS**

### **a. Methods and Procedures**

**Study Overview:** We propose a prospective, large, PRAGMATIC, randomized trial to study the impact of MET and healthy lifestyle intervention (LIFE) vs. LIFE alone on patient-centered outcomes of body weight, SGA-adherence and satisfaction, psychiatric symptom burden (e.g. mood/anxiety), and QoL. We will also examine metabolic outcomes.

The focus of the pragmatic trial is to determine which intervention is most effective through observation of care as usual conditions or in “real-world clinical settings” rather than under controlled experimental circumstances. Information should be collected when available as part of routine clinical practice rather than through study-specific procedures, with minimal interference to clinical practice. Adherence to protocol recommendations from practitioners and patients are observed and documented throughout the study.

**Subjects:** We propose to recruit approximately 1800 overweight/obese youth with BSD who are prescribed SGAs from at least 40 public and private mental health practices (approximately 900 each from sites under the coordination of University of Cincinnati, Midwestern center and from within the sites under the Northwell Health East Coast coordinating center), to participate in the proposed patient-centered large pragmatic trial examining the effectiveness of MET and LIFE vs. LIFE alone. Patients will be eligible for study participation if they are:

1. Inpatient or outpatient age 8-19 years inclusive; participants must live with a parent, guardian, or caregiver;
2. Fluent in English;
3. Diagnosed or told by a clinician that they have any of the following bipolar spectrum disorders (BSD): bipolar I, bipolar II, unspecified bipolar and related disorders, Disruptive Mood Dysregulation Disorder (DMDD), cyclothymic disorder, other specified bipolar and related disorders, as well as mood disorder not otherwise specified (if diagnosed in the past as per DSM-IV);
4. Body mass index  $\geq 85\text{th}$  percentile for age and sex by standard growth charts;
5. Received a new or ongoing prescription for at least one SGA (i.e., olanzapine, clozapine, risperidone, quetiapine, aripiprazole, ziprasidone, iloperidone, lurasidone, paliperidone, brexpiprazole or cariprazine) that is not prescribed as a PRN medication

Additionally, patients will be excluded by the following:

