### **Adherence and Treatment Satisfaction Outcomes:**

**Self-Reported Adherence and Barriers:** Caregivers and children will answer standardized questions related to adherence and adherence barriers to taking SGAs, MET (if applicable), and LIFE. Information on missed and partial doses of each medication in the past week will be ascertained. Questions prefaced by non-judgmental language that normalizes non-adherence to treatment will be used. A time period of one week will be used to maximize respondent recall and minimize memory decay.

**MEMS®6 TrackCap/SimpleMed PillBox:** The Medication Event Monitoring Systems (MEMS) [AARDEX Corporation] and the SimpleMED PillBox are electronic monitoring systems that measure the dosing histories of oral medications. They will be used to monitor adherence to SGAs or MET in a sub-sample of 300 patients at a subset of sites. They consist of a standard plastic vial or box with a threaded opening and a closure for the vial that contains a micro-electronic circuit to register the dates and times the bottle/pillbox is opened and closed. Data from the MEMS TrackCap will be downloaded at each study visit. Patients randomized at an inpatient site to MEMS monitoring will only receive this monitoring if they are scheduled to be followed at an outpatient site that was selected for MEMS monitoring; otherwise, the MEMS aspect of the randomization should be disregarded.

**Treatment Acceptability:** A single-item 5-category Likert-type patient report of satisfaction with psychotropic medication regimen (0=not at all satisfied to 4=very satisfied).

**International Physical Activity Questionnaires (IPAQ):** The IPAQ is an instrument for cross-national monitoring of physical activity and inactivity with good reliability and validity for monitoring population levels of physical activity in diverse settings to assess adherence to LIFE physical activity recommendations.

We will also assess food choices and eating habits using questions selected from the Healthworks Nutrition Screener, Satiety and Food Responsiveness using items from the Child Eating Behavior Questionnaire, and Uncontrolled Eating and Cognitive Restraint using items from the 3-factor Eating Questionnaire.

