Type and duration of current/prior SGA treatment and weight gain during SGA treatment: Prior data suggest that the effect of MET may depend on the extent of weight gain during SGA treatment prior to study entry. Site personnel will document weight and height prior to any SGA treatment, specific SGAs received and duration of treatment with each (i.e., by obtaining medical records). For *a priori* analyses of potential heterogeneity of treatment effect (HTE), we will then distinguish SGA-naïve patients (no current or prior SGA treatment as of baseline visit) versus those with any current or prior SGA treatment. Within the latter group, we will compute change in BMI z-score from the start of SGA treatment until baseline and perform HTE analyses to determine whether MET effectiveness varies based on the duration of SGA treatment and/or amount of excess (relative to normal development) weight gained during treatment.

Classification system for psychotropic treatments: We anticipate substantial variation in the specific psychotropic medication regimens prescribed at baseline, and that these treatments will vary over time. SGAs may be prescribed singly or in combination at varying doses, and concomitant treatment with antidepressants, non-SGA mood stabilizers (e.g., divalproex and lithium) and/or stimulants (e.g., for the subset of patients with co-morbid ADHD) will also be common. For our *a priori* analyses of potential HTE depending on pharmacologic treatments other than MET, we have reduced this large set of options to three groups based on available data regarding their weight effects. Our data will provide considerable additional observational evidence about the impact of specific regimens, and we will conduct detailed analyses that may suggest useful *post-hoc* alternative classifications. Our survey data indicate that

risperidone, aripiprazole, and quetiapine will be the three most common SGAs prescribed.

- (1) Mild to Moderate Risk of Weight Gain: Monotherapy with lurasidone, ziprasidone, or aripiprazole.
- (2) High Risk of Weight Gain: Monotherapy with asenapine, iloperidone, paliperidone, quetiapine or risperidone. SGA-naïve patients receiving monotherapy with a group (1) SGA and patients prescribed divalproex or lithium plus a group (1) SGA will be assigned to this group.

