**(See Next Page)**

**Table 2. Schedule of Events.**

The Table of Events is an approximation for when routine clinic visits might occur. In order to adhere to the pragmatic nature of the study, data will only be collected during the patient's regularly scheduled clinical visits and a participant should not be brought in exclusively to conduct study specific visits. No specific study labs will be mandated for study participation, with the exception noted above (i.e., pregnancy test) The lab tests noted in the Schedule of Events are suggested in accordance with clinical practice guidelines for patients receiving SGAs.

Measures	Visit (Approximate Months)										
	SCREEN/ BASELINE	1	2	3	6	9	12	15	18	21	24
Demographics & Clinical Characteristics (P, Y)	X										
Structured Diagnostic Assessment (K-SADS) a (C)	X										
Medication List (C)	X	X	X	X	X	X	X	X	X	X	X
Weight/Metabolic											
Body Mass Index [height and weight] (C)	X	X	X	X	X	X	X	X	X	X	X
Recommended Metabolic Labs [insulin, lipid profile, glucose, hemoglobin A1C] (C)	X b,d, e				X		X		X		X
Treatment Satisfaction											
Treatment Acceptability Questionnaire (Y)	X	X	X	X	X	X	X	X	X	X	X
Adherence											
Adapted Adherence Measure (P & Y)	X	X	X	X	X	X	X	X	X	X	X
International Physical Activity Questionnaire (P & Y)	X	X	X	X	X	X	X	X	X	X	X
Nutrition, Satiety, and Appetite Measures (P & Y)	X	X	X	X	X	X	X	X	X	X	X
MEMs Cap/ SimpleMed Pillbox Upload [300 patient subset] (C)		X	X	X	X	X	X	X	X	X	X
Mood/Anxiety											
PROMIS c Anxiety Short Form (P & Y)	X				X						X
PROMIS c Depression Short Form (P & Y)	X	X	X	X	X	X	X	X	X	X	X
PROMIS c Anger Short Form (P & Y)	X				X						X
Children's Depression-Revised/Selected Items (C)	X				X						X
Young Mania Rating Scale (C)	X	X	X	X	X	X	X	X	X	X	X
Clinical Global Impression-Severity (C)	X	X	X	X	X	X	X	X	X	X	X
Quality of Life (Weight & General)											
Body Weight, Image & Self-Esteem Evaluation, B-WISE (Y)	X				X						X

"Sizing Me Up"/"Sizing Them Up" (P & Y)	X				X						X
Height Weight Self for Viewpoint-Items 5 & 6 (wt. acceptability) (Y)	X	X	X	X	X	X	X	X	X	X	X
PROMIS c Pediatric Peer Relationships- Short Form (P & Y)	X				X						X
PROMIS c Global Health Scale (P &	X	X	X	X	X	X	X	X	X	X	X
Clinical Global Assessment Scale (C)	X	X	X	X	X	X	X	X	X	X	X
Number of School/Work Days Missed [past 30 days] (Y & P)	X	X	X	X	X	X	X	X	X	X	X

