The basic model for outcomes will be a GLMM with change from baseline to either 6- or 24- months as the dependent variable. Independent variables will include fixed-effect terms for randomized treatment group (MET), baseline value of the outcome, and random site effects. For HTE analyses, a baseline value-by-MET interaction (to assess HTE due to baseline status) will be included, and for particular domains additional continuous or categorical covariates and treatment-by-covariate interaction terms will be added to assess HTE. Outcomes within each domain will share the same set of HTE terms, specified in the Specific Aims. Because the subgroups are in general correlated (e.g., duration of SGA treatment, weight gain history and psychotropic weight burden will be correlated with baseline BMI), we will include multiple first-order HTE terms simultaneously (to assess heterogeneity independently attributable to each moderator), but will also fit separate models for each term to gauge the impact of this correlation on our conclusions. Higher-order treatment-by-covariate interactions will not be included a priori, but will be explored with rigorous adjustment for multiple testing, using step-down testing (removing highest-order interaction terms first) or information criteria based on penalized likelihoods to guide model selection.

**Marginal Structural Modeling for Causal Inference:** SA1 concerns the overall and sub-group specific effects of MET on abrogation of weight gain (with changes in BMI z-score from baseline as outcomes) and metabolic health, particularly metabolic syndrome and its component criteria. BMI and adherence measures are obtained at all study visits, so our models for these measures will use all available observations by treating the longitudinal series of changes in these variables and SGA treatment as dynamically dependent on each other. We will use marginal structural models to address this bi-directional dependence, computing the probability of SGA treatment regimen change at each visit within weight gain treatment regimen groups and using appropriately normalized versions of the inverse of the probability as the stabilized weights.

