**Adjustment of Self-Reported Adherence:** Adherence rates for self-report and MEMS (where available) will be calculated as number of treatments/day divided by number of prescribed daily treatments. Truncated MEMs adherence rates (maximum of 100%) will be used in analyses to reduce inflation as a result of overuse or extra openings due to prescription refills. This method has been used successfully in studies assessing electronic monitoring (EM) adherence. Self-reported adherence vastly underestimates adherence as measured by EM. While it is not feasible to use EM for all patients and medications, we will use the statistical relationship between EM and self-reported adherence in a subsample of 300 patients (equal numbers per treatment group, i.e., 100 for SGA adherence who are also taking MET, 100 for SGA adherence who are not taking MET, and 100 for MET adherence, who are

randomly selected the 8 randomization strata) to estimate EM adherence from self-report in the remaining patients. We will regress EM adherence on self-reports, using standard diagnostics to ensure that non-linearity, heterogeneity of variance across the range of adherence, or subgroup-specific regression relationships are included as needed. Predictions that accurately reflect the residual uncertainty can then be generated by multiple imputation, and the resulting complete-sample datasets will be used in primary analyses involving SGA adherence, with sensitivity assessed by parallel analyses using self-report directly.

**Data and Safety Monitoring plan:** The Cincinnati site will provide an independent certified study data monitor who will visit each site prior to study initiation and approximately every 6 months thereafter. The monitor will follow a monitoring plan that includes source data verifying and ensuring compliance with good clinical practices (GCPs), the IRB-approved protocol and other applicable regulatory guidelines, and will report any problems to the site PI and the other clinical staff members. Additionally, adherence to inclusion/exclusion criteria, completion of scheduled assessments, withdrawal/termination procedures, and maintenance of training and certification for all research personnel will be continuously monitored. The monitor will provide written recommendations following each visit to each site. All reports will be reviewed by members of the Steering Committee.

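### Change from baseline cannot be computed for SGA adherence in patients with no SGA prescribed in the week before baseline, so the planned model drops them from the overall adherence contrast

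*Combined protocol and SAP*

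**What the plan says.** Under Analyses of Specific Aims (section E.b), the general model is: "The basic model for outcomes will be a GLMM with change from baseline to either 6- or 24- months as the dependent variable". Its right-hand side is also set: "Independent variables will include fixed-effect terms for randomized treatment group (MET), baseline value of the outcome, and random site effects". The models for heterogeneity of treatment effect add a baseline-by-MET interaction. Under Marginal Structural Modeling there is a second, all-visit approach: "BMI and adherence measures are obtained at all study visits, so our models for these measures will use all available observations". That approach still models a series of changes.

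The part of section E.b on adjusting self-reports gives the definition of the ratio: "Adherence rates for self-report and MEMS (where available) will be calculated as number of treatments/day divided by number of prescribed daily treatments". The self-report looks back one week: "Information on missed and partial doses of each medication in the past week will be ascertained". Table 2 schedules the self-report form at baseline and at every later visit.

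Inclusion criterion 5 admits new starters: "Received a new or ongoing prescription for at least one SGA". The schedule and treatment section defines SGA-naive as "no current or prior SGA treatment as of baseline visit". Previous SGA exposure is a randomisation stratification factor. H2.1 is worded as an overall effect of assignment to MET, at 6 and 24 months. The text available gives no rule for SGA adherence when there is no baseline value.

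**The concern.** The general model needs a baseline value twice: once to form the change score and once as a covariate. That works for BMI z-score, which every patient has at entry. It does not work for an adherence ratio whose denominator is zero. A first-SGA starter was prescribed no SGA doses in the recall week. Handing the patient the form at baseline does not create a value, and nothing true is missing that could be imputed. A previously exposed patient who had stopped and is restarting at baseline is in the same position.

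At stake is what the overall H2.1 adherence result means. Standard software drops rows with an undefined outcome or covariate. The estimate would then describe ongoing users only, although starters were randomised and SGA exposure was stratified. Precision would fall as well. With no stated rule, an analyst might code starters as 0% (merging them with users who took nothing) or 100% (inventing perfect adherence).

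**Working it through.** **Step 1: which patients have a baseline value.** Baseline adherence = doses taken / doses prescribed, over the week before baseline.

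| Patient at baseline | SGA doses prescribed in that week | Baseline adherence | Change score |
|---|---|---|---|
| Ongoing SGA | above 0 | defined | defined |
| First SGA starting at baseline | 0 | 0/0 | undefined |
| Previously exposed, restarting at baseline | 0 | 0/0 | undefined |

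**Step 2: whether another part of the plan supplies the value.** The multiple imputation predicts electronic adherence from self-report. It needs a self-report value as predictor, and the last two rows have none at baseline. The all-visit model is still of changes, with no statement of how a series without a baseline is handled.

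**Step 3: size.** The text available states no power, effect size or SD for SGA adherence, so there is no figure to reproduce. Inputs:
- 1800 patients randomised 1:1, 900 per arm (Randomization).
- Two-sided 0.05 and 80% power on the full sample (assumptions, for illustration).
- SGA-naive share p from 10% to 50% (assumption). The pilot had 18/47 = 38%, but it covered MET-treated youth at one residential facility, so it is an illustration and not an estimate.

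Formulas, with n = 900 × (1 − p) per arm and the same SD throughout:
- Patients lost = 1800 × p.
- Detectable standardised difference = (1.960 + 0.842) × √(2/n).
- Power remaining = Φ(2.802 × √(1 − p) − 1.960).

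| p | Lost | n per arm | Detectable difference | Power remaining |
|---|---|---|---|---|
| 0 | 0 | 900 | 0.132 | 80% |
| 10% | 180 | 810 | 0.139 | 76% |
| 20% | 360 | 720 | 0.148 | 71% |
| 30% | 540 | 630 | 0.158 | 65% |
| 38% | 689 | 555 | 0.168 | 60% |
| 50% | 900 | 450 | 0.187 | 51% |

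Worked line for p = 50%: 2.802 × √(2/450) = 0.187; 2.802 × √0.5 − 1.960 = 0.021; Φ(0.021) = 0.51. With the 90% retention that the plan expects, the detectable differences run from 0.139 to 0.197 and the power column does not change. These counts cover the SGA-naive only. Restarters would add to them, and their number is not given.

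**Step 4: which remedy works.** A data set of 1800 patients was simulated with about 30% naive, no restarters and complete follow-up.

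| Model | Rows used | SE of treatment effect |
|---|---|---|
| Change, baseline as covariate (as planned) | 1266, none naive | 0.98 |
| Follow-up level, baseline still required | 1266, none naive | 0.98 |
| Follow-up level, exposure term, baseline only where defined | 1800 | 0.85 |

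The first two rows give the same treatment estimate, as they must: follow-up = change + baseline, so with baseline as a covariate only the baseline coefficient moves. Replacing the change score alone recovers nobody. The covariate must be recoded too.

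**The case against.** The strongest reply is that the plan never says starters are excluded. It calls this a basic model, and the all-visit approach uses every available observation. If changes there mean visit-to-visit changes from month 1, starters would stay in. That reading is possible, but it is not specified, and it would not give the month 6 and month 24 contrasts of the general model. What stands is that the loss follows from fitting the stated model and is not a declared exclusion.

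A reader might also infer four stronger points that the documents do not support.
- *That electronic adherence cannot be analysed in anyone, because monitoring is first uploaded at month 1.* Ongoing users have a baseline self-report from which an electronic value can be predicted, and parallel analyses on self-report itself are planned.
- *That the change score adds noise in ongoing users.* The baseline is already a covariate, so change and level give the same treatment effect and standard error.
- *That all of Aim 2 is affected.* Treatment satisfaction concerns the whole psychotropic regimen, is collected at baseline, and is not shown to be affected.
- *That the comparison of prevention with intervention is lost.* The Background frames that comparison in terms of weight gain, and BMI z-score has a baseline in every patient. Prior SGA exposure is a listed moderator for weight (H1.2) but not for adherence (H2.2).

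Nor need the loss unbalance the arms, since previous SGA exposure is stratified.

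**Conclusion.** The concern holds for SGA adherence. The stated model cannot be computed for patients with no SGA prescribed in the week before baseline. Fitted as written, it leaves them out of the H2.1 and H2.2 adherence contrasts at both time points. The consequence is a narrower population than the hypothesis claims and a loss of precision. Bias between the arms is not shown.

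That the model fails for these patients follows from the plan's own definitions. The size of the loss rests on the assumed naive share, an unchanged SD and an assumed 80% power on the full sample, so it should be read as a range. SGA adherence is not the primary outcome, and BMI is untouched. The point should still be settled in the SAP before the adherence data are analysed.

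**What to change.** For SGA adherence only, replace the general model as follows.
- Dependent variable: the adherence level at month 6 and at month 24.
- Include randomised group, site, previous SGA exposure (the stratification factor) and an indicator for having an SGA prescribed in the pre-baseline week. The exposure factor alone does not identify restarters.
- Enter baseline adherence only as indicator × baseline value, set to 0 when undefined. Because the indicator is also in the model, this does not treat starters as non-adherent.
- Confine the baseline-by-MET interaction to patients with a defined baseline.
- Say in the all-visit section how the series starts for patients without a baseline.

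The change of outcome and the recoding of the covariate must be made together. Retaining a patient at month 6 or 24 still requires an SGA to be prescribed at that visit, so the SAP should state its rule for that as well.

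The cost is one paragraph of SAP wording and no new data. The effect will be reported as a difference in level over a wider population, which is not the same quantity as the change effect in ongoing users. If that narrower effect is wanted, it can be reported as a labelled subgroup result.

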#### **A. SPECIFIC AIMS**

The specific aim of this study is to address the significant gap in the evidence base for metformin (MET) use in overweight and obese youth with Bipolar Spectrum Disorders (BSD).

The overall objective of this prospective, large, PRAGMATIC randomized trial is to study the impact of MET and healthy lifestyle intervention (LIFE) vs. LIFE alone on patient-centered outcomes of body weight, Second Generation Antipsychotics (SGA) adherence and satisfaction, psychiatric symptom burden (e.g. mood/anxiety), and quality of life (QoL). We will also examine metabolic outcomes.

**Specific Aim 1:** Assess the overall and subgroup-specific impact of MET+LIFE versus LIFE alone on short- (6mo) and long-term (24mo) **weight and metabolic health** in overweight and obese youth with BSD.

**H1.1:** Overall, assignment to treatment with MET will abrogate more weight gain and lead to fewer adverse metabolic outcomes than LIFE alone at 6 and 24 months.

**H1.2:** (Heterogeneity of Treatment Effects [HTE]): MET's effectiveness at abrogating weight gain and components of metabolic syndrome will vary with respect to the following factors (see Patient Population and Background for rationale and prior data): 1) Change in BMI z-score from SGA initiation to baseline (in patients already receiving SGA treatment); 2) Prior exposure to and duration of SGA treatment; 3) Baseline BMI z- score; 4) Baseline psychotropic weight burden (in SGA non-naïve patients; as defined in Measures below); 5) BSD as diagnosed by a structured interview; 6) Age; 7) Type of insurance (public/private); 8) Ethnicity (Hispanic/Non); 9) Baseline insulin resistance (HOMA-IR); 10) Race (African-American (AA) vs non-AA).

**Specific Aim 2:** Assess the overall and subgroup-specific impact of MET+LIFE vs. LIFE alone on short- (6mo) and long-term (24mo) **SGA adherence and treatment satisfaction**, including assessment of how these effects may be mediated by MET effects on weight gain.

**H2.1:** Overall, assignment to treatment with MET will lead to better SGA adherence and greater treatment satisfaction than LIFE alone after both 6 and 24 months.

**H2.2:** (HTE): MET effectiveness with regard to SGA adherence will vary with respect to: 1) Baseline weight acceptability; 2) Baseline psychotropic medication treatment acceptability; 3) Type of insurance (public/private).

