**H2.3:** The overall effects of MET treatment on SGA adherence will be mediated by degree of weight abrogation, and this relationship will be stronger among girls than boys. We anticipate a possibly complex relationship between abrogation of weight gain (associated with MET) and SGA adherence, because weight gain may also be avoided via SGA non-adherence (at the probable cost of sub-optimal psychiatric outcomes; see Specific Aim 3). A statistical framework (marginal structural models) to accommodate this possibility is described in the Statistical Analysis Plan.

**Specific Aim 3:** Assess the overall and subgroup-specific impact of MET+LIFE vs. LIFE alone on **psychiatric symptom burden, psychotropic treatment changes, and overall and weight-related QoL**, including assessment of how these effects are mediated by MET effects on weight gain and SGA adherence.

**H3.1:** Overall, assignment to treatment with MET will be associated with lower psychiatric symptom burden, decreased risk for symptom-driven treatment changes, and greater improvements in overall and weight-related QoL than LIFE alone at both 6 and 24 months, post-randomization.

**H3.2:** (HTE): MET effects on psychiatric symptoms will be smaller in patients who meet full DSM criteria for a BSD.

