### C. PRELIMINARY STUDIES

**Pilot naturalistic study:** 47 youth with a BMI > 85%ile and prescribed an SGA were treated with MET at CCHMC's residential treatment facility, using a MET dose titrated to 850 mg 2x/day over 2-4 weeks, with a further increase to 1000 mg 2x/day by 2 months if weight gain continued. BMI z score was the primary outcome measure. Electronic medical record data from two groups of these MET-treated patients were analyzed (MS submitted for publication): Group 1 (SGA non-naïve) was taking SGAs for at least 2 months (mean  $\pm$  SD = 9.2  $\pm$  7.2 months, range= 2.3 - 24.9) prior to MET initiation (n=29, 47% girls, age=13.9 years  $\pm$  2.5); Group 2 (SGA naïve) started on MET and SGAs simultaneously (n=18; 59% girls, age=14.2 years  $\pm$  2.8). The groups were similar, and, as in our previous report, 40% received > 1 psychotropic medications. 80% of the SGA non-naïve patients had weight gain > 7% over the 2 months prior to MET initiation and exhibited a 0.45 sd increase in their BMI z score (Figure 1). Surprisingly, more of the SGA naïve (94%) than the SGA non-naïve (78%) patients had a BMI > 95%ile at MET initiation. BMI Z score was stabilized by MET in both groups, but there was a significant group by month interaction ( $p=0.003$ , generalized linear model), even after controlling for the higher baseline BMI z score ( $p=0.002$ ).

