1. Patients will be excluded if they have had exposure to a total daily dose of MET 1000 mg bid for at least 2 weeks in the past 3 months;
2. Patients will be excluded if they could not tolerate MET during the recommended titration schedule outlined in the protocol;
3. Major neurological or medical illnesses that affect weight gain (e.g., unstable thyroid disease) or require a systemic medication that might impact weight or glucose regulation (e.g., diabetes mellitus [insulin], chronic renal failure [steroids]);
4. If lab results are available in the last 6 months, then a fasting serum glucose  $\geq 126 \text{ mg/dL}$  on two occasions prior to or during screening, indicating need for prompt treatment.
5. If lab results are available in the last 6 months, then a serum creatinine  $\geq 1.3 \text{ mg/dL}$  on two occasions during screening and/or follow-up, indicating potential impairment of renal functioning
6. Pregnant or breast feeding;
7. Based on their clinician's assessment, children and caregivers who are unable to complete screening/baseline assessments for any reason;

The enrollment rate will be approximately 1-2 patients/month/site for a recruitment time of 57 months.

**Randomization:** We will randomize 1800 patients (1:1 ratio) to either MET + LIFE or LIFE alone. All patients will receive a lifestyle intervention (LIFE) of brief standardized education. Once a patient is determined to meet the above criteria and has provided appropriate informed consent/assent, site staff will assign the participant a patient ID number. The site staff will then log on to the study's REDCap site and enter the Patient ID, and the following stratification factors: site, overweight or obese, previous SGA exposure, and sex of patient (transgendered patients will be randomized according to sex assigned at birth). REDCap has a built in mechanism that prevents duplication of subject ID numbers.

Once all stratification factors have been entered, the REDCap randomization module will return the next assignment for the appropriate strata.

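### The basic model for the overall treatment effect omits three of the four randomisation stratification factors (overweight/obese, previous SGA exposure, sex): a small loss of precision that costs almost nothing to repair, not a validity error

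*Combined protocol and SAP*

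**What the plan says.** Section E.a (Methods and Procedures), under Randomization, has site staff enter "the following stratification factors: site, overweight or obese, previous SGA exposure, and sex of patient" into REDCap before assignment. After that, "the REDCap randomization module will return the next assignment for the appropriate strata". Block size is not stated.

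Section E.b (Data Analysis and Data Monitoring), under Analyses of Specific Aims, sets out the basic model for change from baseline to 6 or 24 months: "Independent variables will include fixed-effect terms for randomized treatment group (MET), baseline value of the outcome, and random site effects". Further terms come in only for heterogeneity of treatment effect (HTE): "For HTE analyses, a baseline value-by-MET interaction (to assess HTE due to baseline status) will be included", with domain-specific covariates and interactions added for the same purpose.

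The HTE lists in section A (Specific Aims) do not close the gap:
- H1.2, for weight and metabolic outcomes, includes baseline BMI z-score and "Prior exposure to and duration of SGA treatment", but not sex.
- H2.2 reads "MET effectiveness with regard to SGA adherence will vary with respect to: 1) Baseline weight acceptability", followed by treatment acceptability and insurance type. It contains none of the three factors.
- H3.2 reads "MET effects on psychiatric symptoms will be smaller in patients who meet full DSM criteria for a BSD". It contains none of them either.
- Sex appears only in the mediation hypothesis H2.3.

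No section adds overweight/obese status, previous SGA exposure or sex to the overall comparison.

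**The concern.** Factors are chosen for stratification because they are expected to predict outcome, and the usual practice is to carry them into the analysis. The protocol itself treats one of them as prognostic. Section B (Background and Significance) says SGA-related weight gain varies with prior exposure and may be greater in treatment-naïve youth. The psychotropic classification under Study Schedule and Treatment moves SGA-naïve patients on monotherapy with a lower-risk SGA up one weight-gain risk class. Previous exposure is nevertheless absent from the overall-effect model.

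What is at stake is precision. Outcome variation that these factors could explain stays in the residual, so the reported standard error is larger than it needs to be. How much of that is real imprecision, and how much is a standard error that fails to credit the balance the design achieved, depends on how the randomisation lists were built.

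**Working it through.** **Inputs from the documents.** N = 1800, 1:1, about 40 sites, about 90% retention over two years (1620 patients, 810 per arm). Three binary factors beside site give 2×2×2 = 8 cells; crossed with 40 sites, 320 cells of 1800/320 = 5.6 patients on average.

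**Assumptions.** Partial R² of the three factors given baseline value and site: 1, 5 or 10%, with 0% as the floor. Two-sided 5% test. Basic-model power of 80%, for illustration only. For the simulations: blocks of 4 within site-by-factor cells, 45 patients per site, prevalences 70/75/50%. The text supplied gives no alpha, power, target difference or SD for the 1800, so there is no planned power figure to reproduce.

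**1. Reported standard error, continuous outcomes.** Ratio without/with the factors = 1/√(1−R²):
- R² 1%: 1/√0.99 = 1.005
- R² 5%: 1/√0.95 = 1.026
- R² 10%: 1/√0.90 = 1.054

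**2. Unblocked allocation.** The whole ratio is real imprecision. Equivalent patients = 1800×R² = 18, 90, 180. Power with the factors = Φ((1.96+0.842)/√(1−R²) − 1.96) = 80.4, 82.0, 84.0%. Simulated test size was 5.1 to 5.2% with or without the factors.

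**3. Blocks of 4 within cells.** Simulation under a null effect (60,000 trials per R² value, Monte Carlo error 0.09 points on test size):

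| Partial R² | Reported SE ratio | True SE ratio | Test size without factors |
|---|---|---|---|
| 1% | 1.0049 | 1.0010 | 4.84% |
| 5% | 1.0259 | 1.0061 | 4.53% |
| 10% | 1.0540 | 1.0129 | 4.11% |

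With the factors the size was 4.95%. Real information lost = 1800×(1 − 1/ratio²), using the true ratio: about 4, 22, 46 patients. The remainder is overstatement, c = reported ratio/true ratio = 1.0039, 1.0197, 1.0406. If the basic model has 80% power, power with the factors = Φ(true ratio×(1.96c + 0.842) − 1.96) = 80.3, 81.5, 83.1%.

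**4. Cost if the factors explain nothing.** 1/√(1 − 3/(N−1)) − 1 = 0.08% at N = 1800 and 0.09% at N = 1620.

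**5. BMI z-score.** Baseline BMI z is already in the model. Under assumed truncated-normal scores it explains 46 to 66% of the variance of the overweight/obese indicator. The score is also sex-adjusted by construction. Section C (Preliminary Studies) gives 24-week changes of −0.088 with metformin and +0.040 in controls, a difference of 0.128. If the 0.5 printed after the pilot's 0.27 decrease is an SD, SE = 0.5×√(2/810) = 0.0248 and power = Φ(0.128/0.0248 − 1.96) = 99.9%. An assumed difference of 0.06 gives 67.5%, and adding the factors would give about 70% (R² 5%) or 72% (R² 10%) under unblocked allocation.

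**6. Yes/no outcomes.** With assumed control risk 20 to 30%, conditional odds ratio 0.75 and latent R² of 1, 5, 10%, the odds ratio without the factors is 0.751, 0.755–0.757, 0.760–0.763. Adding the factors therefore shifts the target slightly. A standardised risk difference keeps its target; its SE without the factors is 0.2–0.3, 1.1–1.6, 2.3–3.1% larger.

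**7. Missing data.** In a hypothetical stress case, retention was 90/70% by sex in one arm and 70/90% in the other. The model without the factors was biased by 0.030 SD (R² 5%) or 0.046 SD (R² 10%), with test size 8.2% and 13.2%. With the factors, bias was within about 0.002 SD and size was 4.1% and 5.4%.

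**The case against.** The strongest reply is that little may be gained. The partial R² is unknown and could be zero. On the primary outcome, baseline BMI z and a sex-adjusted score leave mainly previous SGA exposure uncovered. The pilot evidence for that factor is a group-by-month interaction that persisted "even after controlling for the higher baseline BMI z score", in 47 patients all taking metformin, so it cannot separate prognosis from a different response. Prior exposure is already a moderator in the Aim 1 HTE model. For adherence, satisfaction, symptoms and quality of life the documents offer no evidence that any of the three factors is prognostic. The plan also calls this the basic model and speaks of the statistical analysis plan as still being completed.

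Most of this stands and keeps the severity low. It does not remove the point: the HTE model is not the overall comparison, and a plan open to completion still states a covariate list without these factors.

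A reader might infer more than the documents support:
- **That the test is invalid or its error rate inflated.** Under balanced allocation the test is mildly conservative; under unblocked allocation its size is right.
- **That up to 180 patients' worth of information is lost.** That holds only for unblocked allocation at an assumed R² of 10%. The protocol does not state the block size.
- **That the same figures apply to the marginal structural models for BMI and adherence.** The covariates of those outcome models are not stated, and nothing here quantifies them.

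**Conclusion.** The point holds as a free improvement of low severity for continuous outcomes. The analysis does not follow the stratified design, and the consequence is a reported standard error up to about 5% too large over the assumed range. Depending on how the lists were built, that is either real lost precision or mostly an overstated standard error, and the documents do not settle which. On BMI z-score the practical effect is probably small, and the omission there is mainly previous SGA exposure. The statement that there is no bias requires complete outcomes, or missingness that does not differ by arm within these factors. The protocol expects incomplete visits, so this condition matters; the stress case is hypothetical but supports the same change. All sizes rest on assumed R², block size, prevalences and starting power.

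**What to change.** In the basic model of section E.b, prespecify fixed effects for overweight/obese, previous SGA exposure and sex, using the values entered at randomisation, and keep the baseline value of the outcome and the random site effect. For yes/no outcomes with a logit link, add one sentence: either the conditional odds ratio is the intended target, or a standardised risk difference from the same model will be reported.

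The cost is two or three sentences in the plan and three degrees of freedom. No new data are needed, because all three factors are in REDCap before assignment.
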